ADVANCES IN MECHANISMS Advances in understanding the role of cutaneous HCQ deposes acquired after prolonged previous treatment in maintaining drug-induced TLRs-7 and -9 inhibition would justify reducing the therapeutic dose based on the drug's immunomodulatory mechanisms of action.

SAMPLE SIZE

The sample size was calculated based on the difference in Reactivation of SLE/SJS in one year after the removal or maintenance of hydroxychloroquine, as observed in the study by Tsakonas et al., 1998 and assuming: 95% confidence interval, α error of 5%; power of 80%; expected success rate after 1 year in the group that kept HCQ at the standard dose (Tsakonas et al., 1998)- 84%; expected success rate after 1 year in the group that fully removes HCQ (Tsakonas et al., 1998)- 59%; no-inferiority margin- 50% of the difference between maintaining chloroquine or removing it completely, i.e., delta of 12%; losses- 10%; n in each group- 128; total number of patients to be recruited: 256 (for SLE/JSLE).

statistical analysis The comparison of the risk of inflammatory activity of the disease in patients using standard dose (HCQ 400 mg/day) vs. patients with reduced dose (HCQ 400mg/day - 3X week) will be made through a survival curve by the log-rank test. The categorical variables will be evaluated by fisher's exact or chi-square test and quantitative variables by student and mann-whitney t tests, when applicable.

TITLE OF THE SUBPROJECT 1C

Prospective study of the pharmacokinetics of hydroxychloroquine in patients with Systemic Lupus Erythematosus using attack dose diseases SLE and JSLE.

Justification

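### Subproject 1B: 128 per arm gives the stated 80% power only at one-sided 5%; judged by a conventional two-sided 95% interval, power is about 70%

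*Combined protocol and SAP*

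**What the plan says.** Subproject 1B is described under STUDY DESIGN as a randomised non-inferiority study with one year of follow-up. Its SAMPLE SIZE paragraph gives these inputs:

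- Error rate and power, running on to the standard-dose rate: "95% confidence interval, α error of 5%; power of 80%; expected success rate after 1 year in the group that kept HCQ".
- Standard dose: "expected success rate after 1 year in the group that kept HCQ at the standard dose (Tsakonas et al., 1998)- 84" percent.
- Full withdrawal: "expected success rate after 1 year in the group that fully removes HCQ (Tsakonas et al., 1998)- 59" percent.
- Margin: "no-inferiority margin- 50% of the difference between maintaining chloroquine or removing it completely, i.e., delta of 12" percent.
- Losses and size: "losses- 10%; n in each group- 128; total number of patients to be recruited: 256 (for SLE/JSLE").

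No success rate is given for the reduced-dose arm, and nothing says whether the 5% is one- or two-sided. The statistical analysis text that follows compares the arms by a survival curve and log-rank test. It does not mention an interval to be compared with the margin.

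**The concern.** A non-inferiority sample size depends directly on the one-sided error rate. A two-sided 95% interval carries 2.5% on the side that matters; a one-sided 5% test corresponds to a two-sided 90% interval. A 95% confidence level quoted beside an α of 5% can be read either way, and the two readings lead to different sample sizes and different power.

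The conclusion at stake is whether the reduced dose can be used without more flares. If the analyst reports a two-sided 95% interval, the chance of missing non-inferiority when the arms are truly equal is about 30%, not the planned 20%. If the analyst uses a 90% interval, the chance of a false non-inferiority claim at the margin is 5% rather than 2.5%, and the plan has not told the reader which applies. If the choice is left until results are known, it can decide the conclusion.

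**Working it through.** **Inputs.** From Subproject 1B, SAMPLE SIZE: control success 0.84, margin 0.12, power 80%, losses 10%, 128 per arm. Assumption, not in the plan: true success on the reduced dose is also 0.84.

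**Formula for evaluable patients per arm.** n = (z_α + z_0.80)² × 2 × 0.84 × 0.16 / 0.12², where 2 × 0.84 × 0.16 = 0.2688 and 0.2688 / 0.0144 = 18.667.

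**Reproducing the plan's figure.**

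- One-sided 5%: (1.645 + 0.842)² × 18.667 = 115.4 evaluable; 115.4 / 0.9 = 128.2. This matches 128. (Rounding up to 116 first gives 128 or 129, depending on how losses are added.)
- One-sided 2.5%, the lower limit of a two-sided 95% interval: (1.960 + 0.842)² × 18.667 = 146.5 evaluable; 146.5 / 0.9 = 162.8. This does not match.

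Other routes also miss 128. With a 12.5-point margin and losses added, the size is 118–119 at one-sided 5% and 150–152 at one-sided 2.5%. A superiority comparison of 84% with 72%, before losses, needs 147 (one-sided) or 186 (two-sided) per arm.

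**Power at the planned size.** Power = Φ(margin / SE − z_α), with SE = √(0.2688 / n). After 10% losses, 128 × 0.9 = 115.2, so n is about 115 and SE = 0.0483.

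| Evaluable per arm | Margin | One-sided 5% | One-sided 2.5% (two-sided 95% interval) |
|---|---|---|---|
| 115 | 12 points | 79.9% | 69.9% |
| 128 (no losses) | 12 points | 83.5% | 74.5% |
| 115 | 12.5 points | 82.7% | 73.4% |
| 128 (no losses) | 12.5 points | 86.1% | 77.9% |

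The 12.5-point rows use half of 84 − 59 = 25 without rounding down to 12. With a restricted maximum-likelihood (Farrington–Manning) variance and the 12-point margin, the two-sided 95% figures are 68.1% at 115 and 72.8% at 128. No variant in the right-hand column reaches 80%.

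**The same wording in Subproject 1C.** Its SAMPLE SIZE paragraph uses nearly the same statement of confidence level, α and power, with 34% against 55%, 10% losses and n = 96. The pooled two-proportion formula gives 86.7 per arm at two-sided 5%, and 86.7 / 0.9 = 96.4. At one-sided 5% it gives 68.2, and 68.2 / 0.9 = 75.8. So 96 is matched by a two-sided calculation per arm. Subproject 1C calls 96 the total, which neither calculation gives, so this is supporting evidence only. It suggests that the phrase does not carry one fixed sidedness through the document.

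**The case against.** The strongest reply is that non-inferiority is a one-sided question. A one-sided test at α = 5% pairs naturally with a one-sided 95% confidence bound, and on that reading the confidence level, α, power and 128 all agree. That 128 fits only this calculation is itself evidence of what was done. This stands: a reader might infer that 128 was miscalculated, and the documents do not support that. It does not settle the matter, because the plan never says one-sided, and an analyst asked for a 95% confidence interval would ordinarily compute a two-sided one.

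Three other stronger readings also fail:

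- **That the plan fixes a two-sided 95% interval as the decision rule.** It does not. The phrase appears only among the sample-size inputs, and the analysis text names a log-rank test. Neither 80% nor 70% is the power of that test; both belong to a comparison of 12-month proportions against the margin.
- **That the plan states 84% in both arms.** It gives 84% for standard dose only. Equality is an assumption, although with it the plan's own figure is reproduced.
- **That the plan conceals its error rate.** It states 5%; what is missing is the sidedness.

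It is also fair to say that 70% is towards the low end of the range. It takes the full 10% loss and the rounded margin, and milder conditions give up to 77.9%. The plan itself budgets for those losses and states that margin, so 70% is the figure that corresponds to its own inputs.

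**Conclusion.** The concern holds as a mismatch between the stated confidence level, read in the ordinary two-sided way, and the stated power. At 128 per arm with 10% losses and a 12-point margin, power is 79.9% at one-sided 5% and 69.9% with a two-sided 95% interval, a gap of 10 percentage points. Across the variants checked, the second figure runs from 68.1% to 77.9%. All of these assume equal true success of 84%; a lower true rate on the reduced dose would reduce power further. If a one-sided 5% test was intended, 128 is right and only the statement of the rule needs repair.

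**What to change.** In the SAMPLE SIZE and statistical analysis text of Subproject 1B, state the non-inferiority rule as the confidence limit for the difference in 12-month success compared with the 12-point margin. Sidedness alone is not enough, since the log-rank test named there does not use the margin. Then state a power that matches, by one of two routes:

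1. a two-sided 95% interval, with power at 128 per arm restated as about 70% after 10% losses; or
2. an explicit one-sided 5% test, using the lower limit of a two-sided 90% interval, with 80% power.

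The assumed success rate in the reduced-dose arm should be written down in either case. The choice should be recorded before outcome data are examined. The change is a sentence or two and needs no extra patients. Its price is a less favourable stated power under the first route, or an openly stated one-sided 5% error rate under the second.

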SUBPROJECT 1B

Prospective, randomized and controlled study comparing the frequency of SLE and jSLE activity of patients with a stable dose of HCQ and patients with dose reduction of this drug and its correlation with blood levels of its metabolites diseases.

SLE AND jSLE

Background

It takes at least 6 months of HCQ use to achieve its best efficacy (Clark et al., 1993). In SLE, regular use of HCQ promotes a decrease in inflammatory outbreaks of the disease (Ruiz-Irastorza et al., 2010) and its withdrawal is associated with worsening activity remission (Tsakonas et al., 1998 - The Canadian Hydroxychloroquine Study Group). Its action is due to a modulating effect on the immune response, influencing the presentation of antigens and production of pro-inflammatory cytokines, which are probably mediated mainly by inhibition of Toll-like receptors-7 and -9 (Wallace et al., 2012). Adequate serum levels of HCQ metabolites are related to a better efficacy in the treatment of the cutaneous form of lupus (Francès et al., 2012) and HCQ concentrations in the blood lower than 1,000 ng/mL determined by HPLC have been associated with higher inflammatory activity of SLE (Costedoat-Chalumeau et al., 2006). Monitoring of HCQ in the blood would allow assessing whether, after a prolonged period of treatment, which causes a tissue deposit of the drug in the skin, a reduction in the weekly dose would be possible. In addition, the measurement of HCQ in saliva could offer a good alternative for blood levels, because it is less invasive, as previously demonstrated with other drugs (Ruiter et al., 2012). The goal for reduced HCQ dose is to avoid retinopathy with vision loss, without risk of increased outbreaks of disease activity. Retinopathy is the most feared side effect of HCQ use and is associated with the cumulative dose of antimalarial (Wolfe et al., 2010). The new recommendation of the American Ophthalmology Association of 2011 determines that ophthalmological control of the use of antimalarials must necessarily include campimetry and at least one more objective examination such as multifocal electroretinogram, optical coherence tomography (SD-OCT) (Marmor et al., 2011). Our objective is to determine the mechanism of HCQ-induced injury through an evaluation of the correlation of functional and structural retinal damage, evaluated by central visual field examination (campimetry) and SD-OCT measurements, with segmentation of the outer layer of the retina (pigment epithelium). The proposed acquisition of a campimeter dedicated to the research intends to validate the isolated use of campimetry, limited to the 10-2 Humphrey field, as the gold standard of this evaluation.

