
In addition, it is extremely important to evaluate whether the reduction of the weekly dose of HCQ after a long period of use of this therapy would be able to maintain inhibition of TLR-7 and -9.

Objectives primary:

- Compare the frequency of outbreaks of disease activity (SLE and jSLE) in patients using standard dose (HCQ 400 mg/day) vs. patients with reduced dose (HCQ 400 mg/3X week) and its correlation with blood and saliva levels of the drug. Secondary: - Compare frequency of retinopathy in patients using standard dose (HCQ 400 mg/day) vs. patients with reduced dose (HCQ 400 mg/3X week) and its correlation with HCQ blood levels.

- Verify a possible longitudinal correlation of HCQ concentrations with the production of interferon-alpha and TNF by plasmacytoid dendritic cells.

- Correlate blood and salivary levels of HCQ and its metabolites in patients with SLE and JSLE with adherence to this treatment.

- Correlate functional and structural damage of the retina, evaluated by central visual field examination (campimetry) and SD-OCT measurements, with segmentation of the outer layer of the retina (pigment epithelium).

- Establishment of a pharmacokinetic-pharmacodynamic model of hydroxychloroquine dose reduction in patients with SLE.

NUMBER OF INDIVIDUALS

Total number of patients required for the study= 256 (SLE and JSLE).

STUDY DESIGN

Randomized controlled prospective study of non-inferiority of one year of follow-up of patients with SLE and JSLE in remission with HCQ use (stable dose of 400 mg/day for at least five years).

Patients will be randomized into two groups: no daily dose reduction group (HCQ 400 mg/day) and reduction group (HCQ 400 mg/day - 3X week). Patients will be evaluated for the activity of the underlying disease in a "blind" way. HCQ concentrations will be measured at the entrance, 6 months and 12 months after.

The groups will be compared for episodes of disease activity (clinical and laboratory parameters). The production of interferon-alpha and TNF by plasmacytoid dendritic cells will be evaluated in the same period in a subgroup of patients.

The following indexes will be used to assess disease activity:

- SLE and JSLE: SLEDAI-2K (Gladman et al., 2002) and active disease randomly defined as SLEDAI-2K \geq 6.

- Renal activity: BP, urine type I, protein and creatinine in an isolated urine sample, serum creatinine, C3, C4, anti-dsDNA, according to the recommendations of the ACR (Hahn et al., 2012).

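### Subproject 1B is sized as a non-inferiority trial on a 12-point margin, but its analysis names only a log-rank test of difference and never uses the margin

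*Combined protocol and SAP*

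**What the plan says.** All references are to Subproject 1B in the combined protocol and SAP.

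- **Background** gives the purpose: "The goal for reduced HCQ dose is to avoid retinopathy with vision loss, without risk of increased outbreaks of disease activity".
- **Study design** calls it a "Randomized controlled prospective study of non-inferiority of one year of follow-up".
- **Sample size** lists its inputs as "assuming: 95% confidence interval, α error of 5%; power of 80%; expected success rate after 1 year", with 84% success expected on the maintained dose and 59% after full withdrawal. It sets a "no-inferiority margin- 50% of the difference between maintaining chloroquine or removing it completely, i.e., delta of 12" percent and arrives at "n in each group- 128; total number of patients to be recruited: 256 (for SLE/JSLE").
- **Statistical analysis** states that the risk of disease activity on the standard dose "vs. patients with reduced dose (HCQ 400mg/day - 3X week) will be made through a survival curve by the log-rank test". Categorical and quantitative variables then go to Fisher's "exact or chi-square test and quantitative variables by student and mann-whitney t tests, when applicable".

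The margin appears only in the sample-size paragraph. Nothing in 1B states a non-inferiority hypothesis, an interval for the treatment difference, a comparison with 12 points, or a rule for concluding non-inferiority.

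**The concern.** A non-inferiority trial asks whether any loss on the reduced dose is smaller than the margin. A standard log-rank test asks whether the two curves differ. A non-significant result does not exclude a 12-point loss, so it cannot support a claim that dose reduction brings no unacceptable rise in flares. Fisher's exact and chi-square tests do not fill the gap, because they also test difference.

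The primary conclusion of the randomized comparison therefore has no stated test. If that stays open, the effect measure, the scale of the margin and the confidence level can all be chosen after the data are seen.

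The confidence level is unsettled too. The 95% confidence interval in the sample-size paragraph is an input to the calculation. The same phrase appears for Subprojects 1A and 1C, which are not described as non-inferiority studies. The text does not say whether it is one-sided or two-sided.

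**Working it through.** **Inputs from 1B, Sample size:** reference success 84%, margin 12 points, α 5%, power 80%, losses 10%, 128 per group. No success rate is given for the reduced-dose arm; 84% (no true difference) is assumed below.

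**1. Reproducing the stated sample size.** Per arm, n = (z_α + z_β)² × 2 × 0.84 × 0.16 / 0.12².

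- One-sided 5%: (1.645 + 0.842)² × 0.2688 / 0.0144 = 115.4, so 116 evaluable. 116 × 1.1 = 127.6, so 128, as stated (116 / 0.9 gives 129).
- One-sided 2.5% (two-sided 95% CI): 146.5, so 147 evaluable. 147 × 1.1 = 161.7, so 162; 147 / 0.9 = 163.3, so 164.
- Half of 84 − 59 = 25 is 12.5, not 12, but a 12.5-point margin does not give 128: it yields 118 or 119 at one-sided 5%, and 150 or 152 at one-sided 2.5%.
- A two-sided test of difference for 84% v 72% would need 186 per arm before losses.

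Of these variants, only a margin calculation at 12 points and one-sided 5% fits the stated number.

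**2. Power of the margin comparison if both arms are at 84%.** Power = Φ(0.12/SE − z), with SE = √(2 × 0.84 × 0.16 / n). Ten percent losses leave 128 × 0.9 = 115 evaluable.

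| n per arm | SE | One-sided 95% limit (z = 1.645) | Two-sided 95% CI (z = 1.96) |
|---|---|---|---|
| 115 | 0.0483 | 80% | 70% |
| 128 | 0.0458 | 83% | 74% |

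**3. One possible result, read both ways.** Take 115 per arm, with 18 patients having disease activity on the standard dose and 26 on the reduced dose.

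- Success: 97/115 = 84.3% v 89/115 = 77.4%; difference −7.0 points (reduced minus standard).
- Tests of difference: log-rank p about 0.18 (events spread evenly over the year), chi-square p = 0.18, Fisher p = 0.24. None shows a difference.
- SE = √[(0.1565 × 0.8435 + 0.2261 × 0.7739) / 115] = 0.0517. The lower limit is −6.96 − 1.645 × 5.17 = −15.5 points (90% CI), or −6.96 − 1.96 × 5.17 = −17.1 points (95% CI).

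Both limits lie below −12, so non-inferiority is not shown.

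**4. How far the two readings can diverge.** Suppose the reduced dose truly loses the full margin (84% v 72%; hazard ratio ln 0.72 / ln 0.84 = 1.88 with exponential times). Simulating 40,000 trials with one year of follow-up and no earlier censoring:

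- The log-rank test is non-significant (two-sided 5%) in about 40% of trials at 115 per arm and 35% at 128. Schoenfeld's formula gives 38% and 34%.
- The margin rule accepts the reduced dose in about 5% of trials (90% CI) or 2.5% (95% CI).

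The plan does not say that a non-significant log-rank test means non-inferiority. These figures show what that reading would cost; they are not an error rate of the plan.

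**The case against.** The strongest reply is that this is incomplete specification and not a wrong method. A log-rank-type test can be run against a null shifted to the margin, and the planned survival curves hold the data for a margin comparison. That is true of survival methods in general. However, the plan names a plain log-rank test and gives no shifted null, bound or rule, so followed as written it does not reach a non-inferiority conclusion.

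Four further points deserve weight:

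- **Sample size.** It is not wrong. It reproduces at one-sided 5%, so the intended sidedness can be inferred, although it is not stated.
- **Dependence on equal rates.** The power figures rest on 84% in both arms. At 115 per arm with a two-sided 95% CI, power is 61% if the reduced arm is truly at 83%, 78% at 85% and 81% at 85.5%. With a one-sided 95% limit it is 73% at 83%.
- **Illustrations.** The 18 v 26 counts were chosen to make the point. The 40% figure depends on a rule the plan does not prescribe, and on continuously observed, exponential flare times.
- **Choice of remedy.** A hazard-ratio margin derived from 84% v 72% would also serve. The primary objective speaks of frequency of outbreaks, which need not mean first events; a 12-month proportion settles that question and should say so.

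These points limit how the illustrations may be read. They do not supply the missing margin comparison.

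**Conclusion.** The concern holds, and it must be fixed before analysis. 1B is labelled and sized as a non-inferiority study, yet every test named in its analysis paragraph is a test of difference. This follows from the text alone and needs no assumption.

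The size of the consequence does rest on assumptions. With 84% success in both arms, the unstated confidence level moves power from about 80% to about 70% at 115 evaluable per arm. With exponential flare times and complete follow-up, treating a non-significant log-rank test as success would accept a true loss of the whole margin in about 35% to 40% of trials, against 2.5% to 5% under a margin rule.

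**What to change.** Rewrite the 1B analysis paragraph so that it states:

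1. **Primary analysis:** the difference, reduced minus standard dose, in the 12-month proportion free of disease activity, estimated from the planned survival curves with its confidence interval.
2. **Decision rule:** non-inferiority is concluded only if the lower limit is above −12 points.
3. **Log-rank test:** supportive only, with a sentence that a non-significant result is not evidence of non-inferiority.
4. **Confidence level, reconciled with the sample size:** either say that 128 per group rests on a one-sided 95% limit (two-sided 90% CI), or, if a two-sided 95% CI is meant, restate power or enlarge the trial. State the success rate assumed for the reduced-dose arm in either case.

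Items 1 to 3 cost only wording and one interval from curves already planned, with no new data. For item 4, assuming 84% in both arms, the one-sided choice leaves 256 patients at 80% power. The two-sided choice means accepting about 70% power (115 evaluable per arm) to 74% (all 128), or recruiting 162 to 164 per group, that is 324 to 328 in total, for 80%.

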- LES and jSLE (ACR criteria) (Hochberg, 1997);
- use of HCQ at a dose of 400 mg/day for at least 3 years.

Exclusion criteria:

- alcoholism;
- renal dialysis;
- concomitant infectious process;
- acute and chronic liver diseases;
- concomitant use of some drugs that interact with HCQ (cimetidine, antacids, digoxin, aminoglycosides, penicillin, neostigmine, pyridostigmine).

RELEVANT METHODS - Ophthalmological assessment: central visual field examination (campimetry) and SD-OCT measurements, with segmentation of the outer layer of the retina (pigmentary epithelium).

- Blood levels of HCQ will be determined by HPLC MS/MS (Munster et al., 2002).

- Pharmacokinetic analysis: The pharmacokinetic parameters of hydroxychloroquine will be calculated in the 24 h dose range based on the total plasma concentration versus time curves. The Winnonlin program, version 4.0 (PharsightCorp., Mountain View, California, USA) and the Non-linear mixed effect level (NONMEM) program will be employed. The area under the plasma concentration curve versus time will be calculated in the 24-h dose interval by the trapezoid method on days 0 and 120. The apparent total clearance (CIT/F) will be obtained through the equation: $CIT/F = Dose/AUC_{0-24}$. The apparent distribution volume (Vd/F) will be calculated by the standard software equation. The hydroxychloroquine-free concentration will be determined by the dosage in saliva. The PK-PD analysis will be performed using as pharmacokinetic parameters the total and free plasma concentrations of hydroxychloroquine and, as a pharmacodynamic parameter, we will use the clinical/laboratory indices obtained by the evaluation of SLEDAI-2K (American College of Rheumatology). The PK-PD model will be developed using the non-linear mixed effect level (NONMEM).

- Others, the same as described in subproject 1A.

Safety

Monitoring of outbreaks of inflammatory activity (flare) and identification of retinopathy.

WITHDRAWALS

Signs of retinopathy.

ORIGINALITY WITH IMPACT on

Healthcare

To date, there is no study demonstrating that the reduction of HCQ dosage after tissue depot caused by a prolonged time of use of the drug can be safely performed in SLEJ and SLE, without increasing the number of outbreaks of inflammatory activity.

The expected care impact is a reduction of severe ophthalmologic event with the reduction of the HCQ dose and the expansion of the time of use of the drug that has a direct impact on the control of disease activity.

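### Subproject 1B: the primary log-rank comparison makes no use of entry SLEDAI-2K, so some precision is probably forgone

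*Combined protocol and SAP*

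**What the plan says.** All references are to subproject 1B of the combined protocol and SAP.

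- **Design.** STUDY DESIGN describes a "Randomized controlled prospective study of non-inferiority of one year of follow-up of patients with SLE and JSLE in remission with HCQ use". Patients are randomised to two groups, and no stratification factor is given.
- **Objective.** The primary objective is to "Compare the frequency of outbreaks of disease activity (SLE and jSLE) in patients using standard dose" against those on the reduced dose.
- **Activity threshold.** The list of activity indices has "active disease randomly defined as SLEDAI-2K" at 6 or above. This is a level, not a change from entry. The same section also looks at episodes through clinical and laboratory parameters and lists a separate set of renal measures.
- **Entry state.** TARGET POPULATION requires the ACR classification criteria and "use of HCQ at a dose of 400 mg/day for at least 3 years". It gives no SLEDAI-2K limit and does not mention remission.
- **Analysis.** The statistical analysis paragraph says that the comparison of the risk of inflammatory activity "will be made through a survival curve by the log-rank test". The only other methods named are simple two-group tests. Multivariate analysis is planned in Project 2 (thalidomide) but not here.
- **Sample size.** 84% success on the standard dose, a 12-point margin, 5% alpha, 80% power, 10% losses and 128 per group.

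**The concern.** Under an absolute threshold, the entry score sets how far each patient is from being counted as active. Someone entering at 4 reaches 6 with a rise of 2, while someone entering at 0 needs a rise of 6. The entry score is then a baseline value of the outcome measure, which makes it the most obvious covariate. Neither the randomisation nor the analysis uses it, and no reason is given.

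What is at stake is precision. If the entry score predicts outbreaks, an adjusted estimate has a smaller standard error from the same patients, and in a non-inferiority comparison the confidence limit then sits further from the margin.

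**Working it through.** **Inputs from 1B, SAMPLE SIZE:** success 84% in both arms under non-inferiority, margin 0.12, power 80%, losses 10%, 128 per group. Sidedness of alpha is not stated. **Inputs not in the documents, so assumed:** the distribution of entry SLEDAI-2K and its prognostic strength.

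**1. Reproduce the plan's figure.** For a difference in proportions at one-sided 5%:

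n = (1.645 + 0.842)² × 2 × 0.84 × 0.16 / 0.12² ≈ 115.4, so 116 per arm.

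With losses, 116 × 1.1 = 127.6, which rounds up to 128 and matches. At one-sided 2.5% the formula gives 147 before losses, which does not match. The plan's 80% is therefore an unadjusted binary calculation at one-sided 5%.

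**2. Unadjusted power.** SE = √(2 × 0.84 × 0.16 / 116) = 0.0481. Power = Φ(0.12/0.0481 − 1.645) = 80.2%. At 115 per arm (128 less 10%) it is 79.9%.

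**3. Effect of adjustment.** If the entry score explains a share R² of the outcome variance, the SE is multiplied approximately by √(1 − R²), so power = Φ(0.12 / [0.0481 × √(1 − R²)] − 1.645).

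| R² | Power, one-sided 5%, 116 per arm | Evaluable per arm for 80% |
|---|---|---|
| 0 | 80.2% | 116 |
| 0.02 | 80.9% | 114 |
| 0.05 | 81.9% | 111 |
| 0.10 | 83.7% | 105 |
| 0.20 | 87.3% | 93 |

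**4. What R² might be.** Take entry scores of 0, 2 and 4 in 50%, 30% and 20% of patients, with overall risk fixed at 16%. Then R² = Σ w(p − 0.16)² / (0.16 × 0.84).

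| Assumed odds ratio per 2 points | Risk at 0 / 2 / 4 | R² | Power |
|---|---|---|---|
| 1.5 | 12.2 / 17.2 / 23.8% | 0.015 | 80.7% |
| 2 | 9.6 / 17.5 / 29.8% | 0.044 | 81.7% |
| 3 | 6.4 / 17.1 / 38.2% | 0.108 | 84.0% |

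With a 70/20/10 mix or equal thirds, R² is 0.012-0.014, 0.039-0.040 and 0.087-0.108, and power is 80.6-80.7%, 81.6% and 83.2-84.0%. If every patient enters at 0, R² is 0 and power stays at 80.2%.

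**5. The log-rank test itself.** Steps 2 to 4 concern the risk difference, the scale of the margin. As a separate check, the two-sided 5% log-rank test against no difference was simulated with 116 per arm, 16% against 28% events, the 50/30/20 mix and 4,000 runs per scenario. Unadjusted and stratified power were 60.6% and 61.2% at a hazard ratio of 1.5 per 2 points, 60.2% and 64.1% at 2, and 59.9% and 68.8% at 3. The direction is the same, but the question tested is a different one.

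**6. Events available.** 2 × 116 × 0.16 ≈ 37.

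**The case against.** The case for leaving the plan alone is substantial, and most of it stands.

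- **The event is not pinned down.** A reader might infer that the log-rank event is the first crossing of 6. The documents do not say so. The analysis paragraph speaks of risk of inflammatory activity, the sample size of reactivation, and the design of clinical, laboratory and renal measures. If outbreaks are judged in another way, the argument about distance from the threshold weakens or disappears.
- **Entry scores may hardly vary.** An undefined remission does not show that every score below 6 is admitted. Patients in remission on long-term treatment may cluster at 0, and the gain then shrinks towards nothing.
- **The unadjusted test is valid.** Randomisation protects the log-rank comparison from bias. A reader might count chance imbalance in entry score as a second harm, but it is already inside the unadjusted standard error. At R² = 0.10 it contributes √0.10 × 4.81 = 1.5 points, and 4.57² + 1.52² ≈ 4.81².
- **Nothing is missing from the stated power.** The 80% assumes no adjustment. Reading the plan's 95% interval as two-sided gives about 70% (70.3% at 116 per arm), but that reflects the alpha level and not the absent covariate.

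What remains is that 1B's only numeric definition of active disease is a level on an index that can be scored at entry, and that using the entry score costs almost nothing.

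**Conclusion.** The point holds as a modest, conditional loss of efficiency. The primary comparison is unadjusted, active disease is an absolute score, and the entry score may vary. If the threshold drives the event, precision is forgone.

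On the basis that reproduces the sample size, the gain in power is plausibly between 0 and about 4 points. That range rests on an assumed odds ratio of up to 3 per 2 points and on assumed score mixes, since the documents supply neither. A larger benefit, such as the 87% at R² = 0.20, needs a stronger gradient than any scenario in step 4 and has no support in the text.

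A reader might conclude that 1B is underpowered or biased because of this omission. The documents support neither conclusion.

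One related matter is larger. A log-rank test of no difference does not test the 12-point margin, with or without a covariate. The fix therefore has to yield an estimate on the margin's scale.

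**What to change.** Before outcome data are seen, amend the 1B statistical analysis paragraph to:

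1. Confirm that the survival event is SLEDAI-2K of 6 or more, or state what else counts, and state whether remission at entry carries a score limit.
2. Fit a Cox model, or another method that handles censoring, with arm and entry SLEDAI-2K. Report the one-year difference in flare risk standardised over the trial population. Plain logistic regression is less suitable, because the plan expects 10% losses and lists signs of retinopathy as a reason for withdrawal. The Cox route still assumes that censoring is uninformative given arm and entry score, and the SAP should say so.
3. Compare the confidence limit of that difference with the 12-point margin and state the confidence level. The sample size matches one-sided 5%, while the text also cites a 95% interval.
4. Keep the unadjusted Kaplan-Meier and log-rank result as a sensitivity analysis.

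The cost is SAP wording, recording the entry score, and one covariate for roughly 37 expected events. No extra patients are needed. If entry scores turn out not to vary, nothing is gained and almost nothing is lost.
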